7.11 Assessment for Depression: Validated 2 question case finding instrument: (1)

“During the past month, have you often been bothered by feeling down,

depressed, or hopeless?" and (2) "During the past month, have you often been bothered by little interest or pleasure in doing things? (telemedicine technology and language assistant may be used)

** labs and tests maybe done 3 weeks prior or up to 3 weeks after clinical baseline/follow-up date (this is defined as acceptable time window)

Above labs and tests from other institutions can be used in lieu of labs done at clinical research site

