2.0 Objectives

The purpose of the study is to evaluate the effect of telotristat ethyl (XERMELO) + somatostatin analog (SSA) (Treatment arm) versus placebo + SSA (standard of care arm) in patients with carcinoid syndrome and carcinoid heart disease. The study will be conducted in agreement with Good Clinical Practice guidelines and the Declaration of Helsinki and be submitted for approval to the MD Anderson Cancer Center IRB before initiation.

Primary Objective:

1. To estimate the percent change in NT-proBNP at 6 month visit from baseline after initiation of study drug in each arm and to compare the percent change between the two study arms.

Secondary Objectives:

1. To evaluate the change in functional capacity from baseline at 3 and 6 month visits as assessed by a 6 minute walk test (6MWT) in each arm
2. To evaluate changes in echocardiographic parameters (CVHD score, global longitudinal myocardial strain assessment of the Left and right ventricle/TAPSE) from baseline to 3 and 6 month visits in each arm
 - a. Carcinoid Valvular Heart Disease (CVHD) score is determined by 1) tricuspid valve appearance, 2) tricuspid regurgitation severity by either spectral pulsed wave or color Doppler flow mapping; 3) pulmonary stenosis severity by spectral pulsed or continuous wave Doppler, and 4) pulmonary insufficiency severity by color Doppler. (Denney et al. JACC 1998)
 - b. Global longitudinal myocardial strain assessment will be conducted using GE Vivid echocardiography machines in all studies. Significant change will be defined as a change in global longitudinal strain by 15%.
 - c. TAPSE will be defined as normal ($\geq 1.6\text{cm}$) or abnormal ($< 1.6\text{cm}$)

3. To evaluate the change from baseline to 3 and 6 month visits in Plasma 5-hydroxyindoleacetic Acid (5-HIAA) levels in each arm. 5-HIAA is a standard test used in clinical practice to assess neuroendocrine tumor (NET) activity.
4. To evaluate the change from baseline to 3 and 6 month visits in high sensitivity troponin T in each arm
5. To evaluate the change from baseline to 3 and 6 month visits in health related quality of life with using the MD Anderson Symptom Inventory (MDASI) in each arm
6. To evaluate compliance of medications

Primary endpoint: The percent change in NT-proBNP at 6 month visit from baseline

Secondary Endpoints:

1. The change in 6MWT from baseline at 3 and 6 months

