6.2.1 Screening Criteria and Randomization plan

Written, Electronic, or Virtual informed consent will be obtained from all patients before beginning any study related screening procedures. The collection of adverse events will begin after patient has received his first dose of treatment. Participants will be allocated to one of two treatment arms by stratified block randomization method, considering age group (≤ 60 years vs. > 60 years) and disease status (with vs. without Carcinoid heart disease) as stratifying factors using Clinical trial conduct website (<https://biostatistics.mdanderson.org/ClinicalTrialConduct>).

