7.0 Baseline Evaluation

- 7.1 Obtain Informed Consent (telemedicine technology and language assistant may be used). We will follow the Office of Clinical Research Standard Operating Procedure (SOP) for informed consent process. During this process, the iConsent feature within EPIC will be utilized. The consent process can be completed either in-person or remote.
- 7.2 Complete history and physical examination including vital signs, NYHA classification, and ECOG (telemedicine technology and language assistant may be used)
- 7.3 CBC with differential, Liver panel (to include AST, ALT, bilirubin, albumin), basic metabolic panel (Sodium, potassium, bicarbonate, chloride, BUN, creatinine, glucose) within 6 weeks (**-asterisk- labs and tests maybe done 3 weeks prior or up to 3 weeks after clinical baseline/follow-up date)
- 7.4 ECG within 6 weeks**
- 7.5 Serum Pregnancy test for females of childbearing age within 1 week
- 7.6 MD Anderson Symptom Inventory MDASI module (in Appendix) within 6 weeks (telemedicine technology and language assistant may be used)**
- 7.7 Echocardiography with a 2D transthoracic echocardiography (2D TTE), 3-dimensional echocardiography (3D TTE), and myocardial strain of the left and right ventricle within 6 weeks**
- 7.8 Plasma 5-HIAA collection within 6 weeks** (it will be kept frozen in Cryogene lab and will be transferred to Frontage Lab for analysis. More information is included in the lab manual.)
- 7.9 Cardiac biomarkers to include: N-terminal pro B-type natriuretic peptide (NT-proBNP) and high sensitivity troponin T (HS-troponin T) within 6 weeks**
- 7.10 6 minute walk test (6MWT) (in Appendix) where distance is recorded in meters within 6 weeks**

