8.13 Study schedule (table)

	Baseline	3 Months**	6 Months**
Clinical /Virtual Clinic Follow-up	X	X	X
CBC with Diff Basic Metabolic Panel (BMP) LFTs	X	X	X
ECG	X	X	X

Pregnancy Test ^ (for females of childbearing age)	X	X	X
Echocardiography (CHD group)	X	X	X
Echocardiography (CS group)	X		X
Plasma collection for 5-HIAA	X	X	X
NT-proBNP	X	X	X
Hs-troponin T	X	X	X
6 minute walk test	X	X	X
MDASI	X	X	X
Depression Assessment	X	X	X

(**-asterisk- labs and tests maybe done 3 weeks prior or up to 3 weeks after clinical baseline/follow-up date. ^- pregnancy test will be within one week of visit)

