11.0 Statistical Consideration

11.1 Sample Size Justification

Primary endpoint is the percent change in NT-proBNP at 6 months from baseline, which is defined as the absolute change divided by the baseline value multiplied by 100. A total sample size of 60 (30 in each group) will be enrolled, accounting for ~13% drop out rate to have 52 subjects with a primary endpoint. Enrolled participants who were dropped out of study will be replaced with additional participants if more than 13% participants were dropped out of the study. A sample size of 30 in each group produces a 95% confidence interval equal to the sample mean change in NT-proBNP plus or minus 10 when the estimated standard deviation is 25, accounting for ~13% drop out rate. There is no preliminary data and there are no similar studies to obtain preliminary estimates for the percent change in NT-proBNP in any of 2 arms.

Therefore, the sample size calculation was performed based on an effect size of 0.8, which is considered as large. Group sample sizes of 30 and 30 achieve 80% power to detect a standard effect size of 0.8 (for example, mean percent difference of 20 when the standard deviation of 25) with a significance level (alpha) of 0.05 using a two-sided two-sample t-test, accounting for ~13% drop out rate. PASS 2005 (Hintze, J. (2004). NCSS and PASS. Number Cruncher Statistical Systems. Kaysville, Utah.

www.ncss.com) was used for the sample size calculation. The caveat is that if the true effect size is smaller than the effect used in power calculation then the calculated sample size will not be enough to achieve 80% power. In case the study turns to be not significant but promising in this setting, these data can be used as preliminary estimates to design a bigger trial.

After enrolling 60 subjects, we evaluated the observed drop-out rate. Three subjects were not randomized yet. Six-month follow-up was not reached for 13 subjects. Sixteen subjects were dropped out of the study (withdrawn prior to randomization (n=6), randomized but withdrawn prior to receiving study treatment (n=4), and randomized, treated, but withdrawn prior to 6-month follow-up (n=6)). Drop-out rate among those who were enrolled, excluding those not reaching 6-month follow-up and those not randomized yet, is 36% (16/44). Since the drop-out rate is higher than 13%, we will enroll additional subjects to replace those who dropped out of the study.

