Among those who received the study drug, 28 subjects have completed 6-month follow-up; 13 subjects were not reached 6-month follow-up yet; 6 subjects were withdrawn prior to 6-month follow-up. 6-month follow-up completion rate among those who received the study drug and reached 6-month follow-up visit is 82% (28/34). At this rate, we expect that 10 of 13 not reaching 6-month will complete 6-month follow-up. To have 52 subjects with a primary endpoint, we still need 14 (i.e., 52-38) additional subjects with a primary endpoint.

Applying the drop-out rate of 36%, we may need to enroll 19 additional subjects in addition to 3 subjects who were not randomized yet. As we enroll additional subjects in the study, we will monitor the number of subjects who complete 6-month follow-up with a primary endpoint. Our goal is to have 52 subjects with a primary endpoint. We will stop enrolling additional subjects once the number of subjects who complete 6-month follow-up with a primary endpoint reaches 52.

If needed, we will evaluate the observed drop-out rate and re-estimate the number of

additional subjects to enroll to have 52 subjects with a primary endpoint after enrolling 19 additional subjects,

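### The plan accepts a baseline NT-proBNP, the denominator of the primary endpoint, up to 3 weeks after the baseline visit and does not tie the baseline value to the first dose, so a compliant baseline can be on treatment

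*Combined protocol and SAP*

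**What the plan says.** Section 11.1 makes percent change in NT-proBNP at 6 months the primary endpoint, "defined as the absolute change divided by the baseline value multiplied by 100". The baseline value is thus both the reference and the denominator.

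Item 7.9 lists the baseline draw as "Cardiac biomarkers to include: N-terminal pro B-type natriuretic peptide (NT-proBNP) and high sensitivity troponin T (HS-troponin T) within 6 weeks". It names no date from which the 6 weeks run, and it carries the double asterisk. The footnote after 7.11 explains the mark: "labs and tests maybe done 3 weeks prior or up to 3 weeks after clinical baseline/follow-up date". It calls this the acceptable window. The footnote to the schedule in 8.13 repeats it, again naming baseline: "3 weeks prior or up to 3 weeks after clinical baseline/follow-up date. ^- pregnancy test will be within one week of visit".

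Three other places bear on when dosing starts:

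- Section 8.14 labels the baseline visit Week 0. It schedules weekly calls from Week 1 that ask about toxicity, adverse events and treatment compliance.
- Section 6.2.1 states: "The collection of adverse events will begin after patient has received his first dose of treatment".
- Section 11.1 records patients who left between enrolment and treatment, including those "randomized but withdrawn prior to receiving study treatment (n=4".

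Section 11.2 sets out the t-test and the adjusted regression for the primary endpoint. It does not say which draw is the baseline value.

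**The concern.** A baseline is meant to describe the patient before treatment. Here the upper end of the window is anchored to a visit and not to the first dose. NT-proBNP is neither an eligibility criterion nor a stratification factor, so no earlier step forces the sample to be taken before dosing.

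If dosing starts near Week 0 and the drug changes NT-proBNP within weeks, a draw in weeks 1 to 3 in the active arm already contains part of the effect. A late draw on placebo does not. The measured difference then moves toward zero. The window is identical in both arms, so the risk is lost power and an underestimated effect, not a false positive.

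The same footnote covers the baseline MDASI, echocardiogram, plasma 5-HIAA, troponin T and walk test (7.6 to 7.10), so the question also reaches the secondary endpoints.

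**Working it through.** **Whether the text allows it.** Read together, 7.9 and its footnote accept a draw at +3 weeks. Section 8.14 asks about compliance from Week 1 and section 6.2.1 begins adverse event collection after the first dose, so dosing by about Week 1 is the natural inference. A draw between then and Week 3 meets the window and is on treatment. No other section overrides this.

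**The plan's own figure.** Section 11.1 gives a difference of 20, SD 25, two-sided alpha 0.05, a two-sample t-test, 80% power and 52 evaluable patients. The noncentral t at effect size 20/25 = 0.8 requires 25.5 per arm, hence 26, and 26 per arm gives 80.7% power. The plan's figure reproduces.

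**Assumptions not in the documents.** True 6-month change of −20% on drug and 0% on placebo. A share *s* of patients has a post-dose baseline. A fraction *f* of the 6-month effect is present at that draw. SD stays at 25.

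**Formulas.**

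- Percent change measured from a post-dose baseline = 100 × [0.8 / (1 − 0.2*f*) − 1]
- Active-arm mean = *s* × (that value) + (1 − *s*) × (−20)
- With linear onset to week 24 and draws spread evenly over weeks 0 to 3, mean *f* = 1.5/24 = 0.0625

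For *f* = 0.0625 the measured change is −18.99. For *f* = 0.25 it is −15.79.

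| Share late | *f* | Difference | Power, 26 per arm |
|---|---|---|---|
| any | 0 | 20.00 | 80.7% |
| 25% | 0.0625 (linear) | 19.75 | 79.8% |
| 100% | 0.0625 (linear) | 18.99 | 76.6% |
| 25% | 0.25 | 18.95 | 76.4% |
| 50% | 0.25 | 17.89 | 71.6% |

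A loss of 5 points (to 75.7%) needs *f* of about 0.65 with 10% late, 0.28 with 25% late, or 0.15 with 50% late.

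**What a tighter window can still recover.** Section 11.1 counts 28 completers and expects 10 of 13 more, so 38, and states: "To have 52 subjects with a primary endpoint, we still need 14 (i.e., 52-38) additional subjects with a primary endpoint". If only those 14 are protected, the late share falls to *s* × 38/52:

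| Share late before the fix | *f* | Share late after | Difference after | Power before | Power after |
|---|---|---|---|---|---|
| 25% | 0.0625 | 18.3% | 19.81 | 79.8% | 80.0% |
| 25% | 0.25 | 18.3% | 19.23 | 76.4% | 77.6% |
| 50% | 0.25 | 36.5% | 18.46 | 71.6% | 74.3% |

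**An analysis that excludes post-dose baselines.** With a quarter of all 52 late, 52 × 0.75 = 39 remain and power at a difference of 20 is 68.2%. With a quarter of only the 38 late, 52 − 9.5 = 42.5 remain and power is 72.1%.

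**The case against.** The strongest reply is that the post-dose step is nowhere stated. The window runs from the clinical baseline date, and the drop-out account in 11.1 shows that enrolment, randomization and first dose are separate steps. Some draws after the baseline visit may therefore still precede dosing. This stands, and it is why the point says that a compliant baseline can be on treatment, not that any was.

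The intent is also probably a pre-dose baseline. The primary objective reads "To estimate the percent change in NT-proBNP at 6 month visit from baseline after initiation of study drug in each arm", sections 7 and 8 separate baseline from on-study evaluation, and the footnote may be generic wording, since item 8.9, which concerns follow-up only, also says baseline/follow-up. That is a fair reading of intent, but the +3 weeks is written as a rule and nothing qualifies it.

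The effect may also be trivial. An SD of 26 instead of 25 would lower power to 77.6%, more than linear onset does with a quarter late, and 11.1 admits that there are no preliminary data. This stands as well. It limits the weight of the point and does not remove the ambiguity.

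A reader might go further and infer that the plan gives no baseline at all. It does label one, Week 0 in 8.14. What is missing is a definition of the baseline value relative to first dose.

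**Conclusion.** The point holds in this limited form and should be fixed. Following the plan exactly can put an on-treatment NT-proBNP in the denominator of the primary endpoint.

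That the text permits this rests on the window wording and on the inference of dosing by about Week 1. The harm rests further on the drug acting on NT-proBNP within those weeks. The documents give neither an onset time course nor the share of late draws. Under linear onset the loss is 1 to 4 points of power. Losses of 5 points or more need either faster onset or pessimistic combinations of late share and early effect that nothing in the documents supports.

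A reader might infer that baselines already collected are contaminated, that the trial has lost material power, or that the result could be biased in the drug's favour. The documents support none of these. No draw dates are given, the loss may be nil, and a window common to both arms moves any early effect toward no difference.

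**What to change.** 1. In 7.9 and the double-asterisk footnotes of sections 7 and 8.13, limit the post-visit part of the window to follow-up visits. Require the baseline NT-proBNP and the other baseline efficacy measures (7.6 to 7.10) before the first dose, with date and time recorded when both fall on the same day; a rule by date alone would still admit a same-day post-dose sample. Replace the unanchored 6 weeks with one look-back limit that ends at the first dose. Keeping 6 weeks would leave the total width as it is now (3 weeks either side).
2. In 11.2, define the baseline value as the last value before the first dose. For patients already treated who have none, use the value accepted under the current window and keep them in the primary analysis.
3. Count post-dose baselines before unblinding. Prespecify a supportive sensitivity analysis that excludes them, and state that its power is low (about 68% to 72% if a quarter are late), so a null result there would say little.

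The cost is protocol wording, one definition and one added analysis. It adds no procedure and no patients, and nobody leaves the primary analysis. The downsides are less scheduling flexibility for patients still to be randomized and possibly somewhat older baselines. The gain in power is modest: 0.2 to 2.7 points in the scenarios above, and less if fewer than 14 evaluable patients remain to be treated. The definition and the count apply to all 52 and settle the rule before the data are seen.

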8.0 Evaluation during Study

- 8.1 Complete history and physical examination done at 3 and 6 months as part of clinical follow-up. (telemedicine technology and language assistant may be used)
**A window of 3 weeks before or after for these visits will be acceptable to accommodate for patient convenience.
- 8.2 CBC with differential, Liver panel (to include AST, ALT, bilirubin, albumin), basic metabolic panel (Sodium, potassium, bicarbonate, chloride, BUN, creatinine, glucose) done at 3 and 6 month (**-asterisk- labs and tests maybe done 3 weeks prior or up to 3 weeks after clinical follow-up date)
- 8.3 ECG done at 3 and 6 months within 6 weeks of clinical visit**
- 8.4 Pregnancy test for females of childbearing age within one week
- 8.5 MDASI done at 3 and 6 months (telemedicine technology and language assistant may be used;can be done within 6 weeks of clinical follow-up)
- 8.6 Echocardiography with a 2D transthoracic echocardiography (2D TTE), 3-dimensional echocardiography (3D TTE), and myocardial strain of the left and right ventricle to be done at 3 and 6 months for those patients with carcinoid heart disease and with carcinoid syndrome and high suspicion of carcinoid heart disease (CHD group), such as those with clinical features or increased NT-proBNP (> 260) mg/ml and/or 5-HIAA levels (24 hr urine 5-HIAA > 100 mg). (**- asterisk- labs and tests maybe done 3 weeks prior or up to 3 weeks after clinical follow-up date
- 8.7 Echocardiography will be done at 6 months in patients with carcinoid syndrome (CS group) who do not have high suspicion for carcinoid heart disease

8.8 Plasma 5-HIAA collection at 3 and 6 months (**-asterisk- labs and tests maybe done 3 weeks prior or up to 3 weeks after clinical follow-up date) (it will be kept frozen in Cryogene lab and will be transferred to Frontage Lab for analysis. More information is included in the lab manual.)

8.9 Cardiac biomarkers to include: N-terminal pro B-type natriuretic peptide (NT-proBNP) and high sensitivity troponin T (HS-troponin T) at 3 and 6 months (**-asterisk- labs and tests maybe done 3 weeks prior or up to 3 weeks after clinical baseline/follow-up date)

8.10 6 minute walk test (6MWT) where distance is recorded in meters at 3 and 6 months (**-asterisk- labs and tests maybe done 3 weeks prior or up to 3 weeks after clinical follow-up date)

8.11 Assessment for Depression at 3 and 6 month (**following window above) clinical follow-up: Validated 2 question case finding instrument: (1) "During the past month, have you often been bothered by feeling down, depressed, or hopeless?" and (2) "During the past month, have you often been bothered by little interest or pleasure in doing things? (telemedicine technology and language assistant may be used)

8.12 Data on hospitalization, death, routine clinical data, and routine imaging data (such as CT scan, MRI, PET, and echocardiography) will be collected and explored with correlation with study interventions

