3.4 Biomarkers in Carcinoid Heart Disease and Carcinoid Syndrome

While clinical signs maybe difficult to assess the role of the cardiac biomarkers has been studied and utilized in both patient with carcinoid heart disease and carcinoid syndrome. Patients with normal NT-proBNP levels have a better survival when they have carcinoid syndrome irrespective of whether or not they have carcinoid heart disease (17). Furthermore, NT-pro-BNP and 5-HIAA levels are independently associated with

symptom status and mortality in patients with metastatic NETs and carcinoid heart disease (26).

Patients with carcinoid heart disease in general have elevated NT-proBNP levels (Median 1,149 pg/ml vs 101 pg/ml) (18) highlighting the prognostic implications of this cardiac biomarker. Lastly, an NT-proBNP level cutoff of 260 pg/ml provides a high sensitivity (92%) and specificity (91%) to detect carcinoid heart disease (18). In fact this NT-ProBNP levels cutoff is being advocated in the Carcinoid Heart Disease expert statement for the screening and investigation of carcinoid heart disease (19).

As serotonin levels are implicated in both carcinoid syndrome and carcinoid heart disease, urinary 5-HIAA levels are also associated with the disease. In fact, a Urinary 5-HIAA level of $>300 \mu\text{mol}/24 \text{ hours}$ is associated with a 2.74-fold increase of the development and progression of carcinoid heart disease (20).

Furthermore, a novel echocardiographic technique, myocardial strain analysis, has some promising applications in patients with carcinoid disease. In a study using the RV free wall strain and tricuspid annular plane systolic excursion (TAPSE), it has been demonstrated that RV function is reduced in patients with intestinal carcinoid disease independent of obvious valvular involvement. This finding, in addition to the fact that patients with and without carcinoid heart disease showed slightly but significantly reduced LV global strain compared with healthy individuals, would suggest that that intestinal carcinoid disease may affect cardiac function before valvular involvement (25) and perhaps the possible role of serotonin in this process.

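### Section 8.6 prints the NT-proBNP criterion for the 3-month echocardiogram group in mg/ml; section 3.4 gives the same cutoff of 260 in pg/ml

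*Combined protocol and SAP*

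**What the plan says.** Section 8.6 assigns echocardiography at 3 and 6 months to two kinds of patient: those with carcinoid heart disease, and those with carcinoid syndrome in whom it is strongly suspected. The second kind is described by example: "high suspicion of carcinoid heart disease (CHD group), such as those with clinical features", followed by the laboratory criteria "increased NT-proBNP (> 260) mg/ml and/or 5-HIAA levels (24 hr urine 5-HIAA > 100 mg".

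Section 8.7 covers everyone else: "Echocardiography will be done at 6 months in patients with carcinoid syndrome (CS group) who do not have high suspicion for carcinoid heart disease". The schedule in 8.13 agrees. The CHD group is scanned at baseline, 3 and 6 months, and the CS group at baseline and 6 months.

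The background in section 3.4 gives the same number with a different unit: "an NT-proBNP level cutoff of 260 pg/ml provides a high sensitivity (92%) and specificity (91" (the last figure is a percentage). It adds that an expert statement supports this cutoff for screening, and it cites median NT-proBNP values of 1,149 pg/ml in carcinoid heart disease against 101 pg/ml in the comparison group.

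**The concern.** One number, 260, carries two units in the same document. Section 3.4 is background. Section 8.6 is the instruction that site staff follow, and it is the text against which a monitor or analyst would check who should have been scanned at 3 months.

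If the printed unit were applied, NT-proBNP could never place a patient in the CHD group. A patient whose only sign of high suspicion was a raised NT-proBNP would fall into the CS group and have no 3-month echocardiogram. That patient would contribute no 3-month CVHD score, strain or TAPSE value to secondary endpoint 2 in section 2.0.

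**Working it through.** **Inputs**

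- Printed threshold: > 260 mg/ml (8.6).
- Cutoff in the background: 260 pg/ml (3.4).
- Medians for scale: 1,149 pg/ml in carcinoid heart disease, 101 pg/ml in the comparison group (3.4).

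**Step 1: put both thresholds in one unit.** 1 mg = 10^-3 g and 1 pg = 10^-12 g, so 1 mg = 10^9 pg.

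260 mg/ml x 10^9 pg/mg = 2.6 x 10^11 pg/ml.

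**Step 2: compare with the cutoff in 3.4.**

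(2.6 x 10^11) / 260 = 10^9.

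**Step 3: compare with the values in 3.4.**

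(2.6 x 10^11) / 1,149 = about 2.3 x 10^8.

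The printed threshold is more than two hundred million times the median in patients who have the disease. In other units it is 260 mg/ml x 1,000 ml/l = 260 g per litre of sample, which is not a possible concentration for this marker. Read literally, the criterion selects nobody.

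**Step 4: check that pg/ml is the intended unit.** With pg/ml, 101 < 260 < 1,149. The cutoff then lies between the two medians, as a discriminating threshold should, and it equals the screening cutoff in 3.4.

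**Step 5: trace who depends on the threshold.** Taking 8.6 and 8.7 together:

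| Patient | 3-month echo if mg/ml is applied | 3-month echo if pg/ml is applied |
|---|---|---|
| Known carcinoid heart disease | yes | yes |
| Suspected, with clinical features | yes | yes |
| Suspected, with qualifying urine 5-HIAA | yes | yes |
| Suspected only because NT-proBNP exceeds 260 pg/ml | no | yes |
| None of these | no | no |

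Only the fourth row changes, and only at 3 months. All patients have a baseline echocardiogram (7.7) and a 6-month one (8.6, 8.7, 8.13).

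**The case against.** The best counter-argument is that this is a self-evident slip. Section 3.4 prints the correct unit next to the cutoff and the medians, and no clinician or laboratory would try to apply 260 mg/ml to NT-proBNP. In practice staff will read pg/ml. The criteria are also examples joined by alternatives, so no single one is required. All of this stands, and it is why the point is minor. It does not make the text right: an operative threshold should be correct where it is stated, without relying on the background section to repair it.

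Three stronger readings are tempting, and the documents do not support them.

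- **The echo-group rule is unworkable.** It is not. The open list leaves the other routes into the CHD group intact.
- **The urine 5-HIAA criterion is also an error, because the study schedules only plasma ("Plasma collection for 5-HIAA" in 8.13).** A routine-care urine result can serve as a sign of suspicion, and a missing one blocks nothing. Saying where the value comes from would be extra detail, not a correction.
- **A definite number of patients will lose their 3-month scan.** One could apply the 9% that a specificity of 91% leaves (100 - 91) to the patients still to come under section 11.1. That would carry a cited study's specificity over to this trial's patients without support. It would also count people who never start treatment: of the 44 with a known outcome, 6 withdrew before randomisation and 4 before treatment, so 44 - 6 - 4 = 34 were treated. The documents do not say how many patients would qualify on NT-proBNP alone.

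**Conclusion.** The NT-proBNP unit in 8.6 is wrong as written, by a factor of 10^9. This rests only on comparing 8.6 with 3.4 and on a unit conversion, and needs no outside figure. Nothing suggests that the text reading caused it: the sentence is ordinary prose, and pg/ml comes through correctly in 3.4.

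The severity is minor. At most, the error could remove 3-month CVHD score, strain and TAPSE values for patients who qualify on NT-proBNP alone, and only if someone applied the printed unit. The size of that group cannot be derived from the documents.

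A reader might infer from the shared label that the error reaches the randomisation stratum for carcinoid heart disease. Section 6.2.1 stratifies on disease status, with or without carcinoid heart disease, and does not refer to the 8.6 criteria, so this does not follow. The primary endpoint, the 6-month percent change in NT-proBNP, does not use the threshold.

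**What to change.** In section 8.6, write the criterion as NT-proBNP > 260 pg/ml, to agree with section 3.4. Nothing else in the echo-group rule needs to change for this point.

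The cost is one corrected unit, which can go into the next amendment. It adds no test, visit, patient or analysis.
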